10.2 Subject Accountability

The number of subjects screened, randomized (in blinded period), receiving IP (in blinded period and OLE), completing the double blind treatment period, and completing the study will be summarized. The number and percent of subjects randomized will be tabulated by the stratification factor and study site.

Double blind treatment period discontinuation, the study discontinuation and IP (in blinded period and OLE) discontinuation will be tabulated separately by reasons for discontinuation.

The number of subjects included in and excluded from each analysis set and reason for exclusion will also be summarized.

Key study dates for the first subject enrolled, last subject enrolled, and last subject's end of study will be presented

10.3 Important Protocol Deviations

Important Protocol Deviations (IPDs) categories are defined by the study team before the first subject's visit and updated during the IPD reviews throughout the study prior to database lock. These definitions of IPD categories, sub-category codes, and descriptions will be used during the course of the study. Eligibility deviations are defined in the protocol.

10.4 Demographic and Baseline Characteristics

Demographics (ie, age, sex, race, cardiovascular medical history, laboratory parameters) and baseline disease characteristics will be summarized by randomized treatment group and overall using descriptive statistics. If multiple races have been reported for a subject, the subject will be categorized as multiple races. Difference in stratum assignment between IVRS/IWRS stratum and data-derived stratum will be tabulated.

10.5 Efficacy Analyses

The following table summarizes the key efficacy analyses that will be conducted.

Table 3. Key Efficacy Analyses Summary

Endpoint	Statistical Analysis Method	P-values from the Statistical Tests	Hierarchical Testing Procedure as Specified in the Multiplicity Adjustment Method Diagram
			Testing of Pooled EvomabTreatment Effect vs. Ezetimibe
Co-Primary Endpoints			

 Mean percent change from baseline at weeks 10 and 12 in LDL-C Percent change from baseline at week 12 in LDL-C 	Repeated measures model	P1 = Maximum of the two p-values for the co-endpoint pair from the primary analysis in FAS	P1 compare to $\alpha = 0.05$
Co-Secondary Endpoints (Tier 1)			

 Mean LDL response (achievement of LDL-C < 70 mg/dL) at weeks 10 and 12 LDL response at week 12 	Cochran Mantel-Haenszel (CMH) test	P2a = Maximum of the two p-values for the co-endpoint pair in FAS	
If P1 < 0.05, \rightarrow P2a and all P2b's will be tested through Hochberg method with $\alpha = 0.005$
 
Else (ie, co-primary endpoint in FAS is not significant) \rightarrow No further testing.

 Mean change from baseline at weeks 10 and 12 in LDL-C Change from baseline at week 12 in LDL-C and Mean percent change from baseline at weeks 10 and 12 Percent change from baseline at week 12 in each of the following lipid parameter: total cholesterol, non-HDL-C, ApoB, total cholesterol/HDL-C ratio, ApoB/ApoA1 ratio 	Repeated measures model	
For each lipid parameter, P2b = Maximum of the two p-values for each co-endpoint pair in FAS
	
Co-Secondary Endpoints (Tier 2)			

 Mean percent change from baseline at weeks 10 and 12 Percent change from baseline at week 12 in each of the following lipid parameters: Lp(a), triglycerides, HDL-C, and VLDL-C 	Repeated measures model	
For each lipid parameter, P2c = Union-intersection test p-value from the two contrasts of each co-endpoint pair in FAS
	
If P2a and all P2b's are significant through Hochberg method, \rightarrow P2c will be tested through Hochberg method with $\alpha = 0.05$.
 
Else (ie, not all tier 1 co-endpoints in FAS are significant), \rightarrow P2c will be tested through Hochberg method with $\alpha = 0.045$.

10.5.1 Analyses of Co-Primary Endpoints

10.5.1.1 Primary Analysis of Co-Primary Endpoints

To assess the co-primary endpoints of the mean percent change from baseline at weeks 10 and 12 and the percent change from baseline at week 12 in LDL-C, a repeated measures linear effects model will be used to compare the efficacy of evolocumab (pooled Q2W and QM) with pooled ezetimibe. The repeated measures model will include terms of treatment group, stratification factor of screening LDL-C level, scheduled visit, and the interaction of treatment group with scheduled visit. Missing values will not be imputed when the repeated measures linear effects model is used.

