10.1.3 Covariates and Subgroups

Baseline covariates include, but are not limited to:

- Stratification factors:
 - Screening LDL-C level: < 180 mg/dL [4.7 mmol/L] vs. ≥ 180 mg/dL
 - Baseline statin use: yes vs. no

The following baseline covariates may be used for subgroup or covariate analyses with the subgroups as specified or in their original format:

- Age: < 65 years, ≥ 65 years; < 75 years, ≥ 75 years
- Sex
- LDL-C: < baseline median, ≥ baseline median
- PCSK9 level: < baseline median, ≥ baseline median
- Baseline lipid regulating medications use: yes vs. no

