3.1 Study Design

This is a phase 3, multicenter, double-blind, randomized, ezetimibe controlled, parallel group study for evolocumab in hypercholesterolemic Japanese subjects unable to tolerate an effective dose of a statin. Subjects who meet all inclusion/exclusion criteria will be randomized with an allocation ratio of 2:2:1:1 into 4 groups: QM 420 mg SC evolocumab + QD PO placebo, Q2W 140 mg SC evolocumab + QD PO placebo, QM SC placebo + QD 10 mg PO ezetimibe, Q2W SC placebo + QD 10 mg PO ezetimibe. Randomization will be stratified by screening LDL-C level and baseline statin use. Randomization should occur within 5-10 days of the screening LDL-C evaluation used to

determine eligibility. Subjects on low or atypical statin therapy must be on a stable dose for at least 4 weeks prior to the screening and throughout the blinded portion of the study; the dose cannot be adjusted during screening and for the duration of the study.

For blinding purposes, every subject will receive investigational product (IP) SC and PO. Patients will be provided with evolocumab or placebo through the use of an autoinjector (AI) or Personal Injector. Depending on availability either a single Personal Injector or 3 autoinjectors will be provided for monthly dosing. A single AI will be used for Q2W dosing. Evolocumab and corresponding placebo will be administered at the study site or at appropriate non-clinic setting per protocol Table 1 (Schedule of Assessment). PO placebo will be available to match PO ezetimibe through over-encapsulation. The SC IP dose frequencies of Q2W and QM will not be blinded.

Following the week 12 visit, all subjects will self-administer IP in the non-clinic setting; subjects will return to the clinical site at W24, W36, W48 and W52 for subsequent visits. There will be an end of study phone call at W54 (Q2W subjects only) for any potential adverse events, serious adverse events, or adverse device effects.

Central laboratory results of the lipid panel, ApoA1, ApoB, lipoprotein(a), and high sensitivity C-reactive protein (hsCRP) will be blinded during double-blind treatment. Investigators will be provided lipid results starting at week 24 until the end of study for each subject. All lipid results from posttreatment to week 24 will remain blinded until the unblinding of the clinical database.

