7.4 Subgroup Analyses

Stratification factors:

- Screening LDL-C level (< 180 mg/dL [4.7 mmol/L] vs. \geq 180 mg/dL)
- Baseline statin use (yes vs. no)

Subgroup by baseline characteristics:

- Age (< 65 years, \geq 65 years; < 75 years, \geq 75 years)
- Sex
- LDL-C (< baseline median, \geq baseline median)
- PCSK9 level (< baseline median, \geq baseline median)
- Baseline lipid regulating medications use (yes vs. no)
- Body Mass Index (BMI) (< 25, 25 - < 30, \geq 30)
- Glucose tolerance status (type 2 diabetes mellitus, metabolic syndrome, neither type 2 diabetes mellitus nor metabolic syndrome)
- Hypertension (yes, no)

- Baseline CHD risk factors ≥ 2 (yes, no)
- Triglycerides (<baseline median, \geq baseline median; $< 150 \text{ mg/dL}$, $\geq 150 \text{ mg/dL}$; $< 200 \text{ mg/dL}$, $\geq 200 \text{ mg/dL}$)
- NCEP (NCEP, 2002) high risk (yes, no)

Subgroup analysis may not be performed if number of subjects in one of the categories is too small for that subgroup variable.

8. Interim Analysis and Early Stopping Guidelines

No interim analysis is planned for this study.

An external independent DMC has been established to formally review the accumulating data from this and other completed and ongoing studies with evolocumab to ensure there is no avoidable increased risk for harm to subjects. The independent DMC is chaired by an external academic cardiologist who is an expert in lipids and clinical trials.

Analyses for the DMC are provided by the Independent Biostatistical Group (IBG), which is external to Amgen. Details are provided in the DMC charter.

9. Data Screening and Acceptance

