10.5.1.2 Sensitivity Analyses of Co-Primary Endpoints

To evaluate the robustness of the primary analysis results, sensitivity analyses will be performed as follows:

- The primary analysis will be repeated on the CAS.
- Non-parametric analyses (Quade test) will be performed on the FAS and CAS.

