10.5.1.3 Subgroup Analyses of Co-Primary Endpoints

Subgroup analyses on the co-primary efficacy endpoints will be conducted using the subgroups specified in [Section 7.4](#). Treatment effect differences among subgroups, which represent subgroup by treatment interactions, will be estimated and tested based on statistics from the subgroup repeated measures models.

For subgroup analyses, the data-derived stratification factor (ie, screening LDL-C level and baseline statin use) will be used.

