10.6 Safety Analyses

10.6.1 Adverse Events

The Medical Dictionary for Regulatory Activities (MedDRA) version 20.1 or later will be used to code all events categorized as adverse events (AEs) to a system organ class and a preferred term. Severity of AEs will be graded using the CTCAE ([Appendix C](#)) and recorded on the eCRF. All adverse event tables will be summarized by actual treatment group. Treatment-emergent adverse events are events with an onset after the administration of the first dose of IP.

The subject incidence of AEs will be summarized for all TEAEs, serious TEAEs, TEAEs leading to withdrawal of investigational product, treatment-related TEAE and fatal TEAEs.

Subject incidence of all TEAEs, serious TEAEs, TEAEs leading to withdrawal of investigational product, and fatal TEAEs will be tabulated by system organ class and preferred term in descending order of frequency.

All TEAEs, serious TEAEs and TEAEs leading to withdrawal of investigational product will also be summarized by subgroups of age (< 65 years, ≥ 65 years; < 75 years, ≥ 75 years) and baseline statin use (Yes, No).

Subject incidence of TEAEs related to a device will be tabulated by preferred term in descending order of frequency.

Subject incidence of adverse events associated with injectable protein therapies:

- Injection site reactions
- Hypersensitivity or allergic reactions

will be summarized by category and preferred term. Neurocognitive events will also be summarized.

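### The primary model leaves out baseline statin use, one of the two stratification factors; the consequence is at most a small, conservative loss of precision

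*SAP*

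**What the plan says.** SAP 3.1 states: "Randomization will be stratified by screening LDL-C level and baseline statin use". Protocol 5.1 agrees, with the LDL-C cut at 180 mg/dL, and Protocol 10.1.3 lists "Baseline statin use: yes vs. no" among the stratification factors.

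SAP 10.5.1.1 then specifies the primary analysis: "The repeated measures model will include terms of treatment group, stratification factor of screening LDL-C level, scheduled visit", and the interaction of treatment with visit. Protocol 10.5.2 has the same terms. Neither document explains why the second factor is absent.

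The model carries forward. The completer-set sensitivity analysis repeats it (SAP 10.5.1.2), and the continuous co-secondary and tertiary endpoints are analysed similarly (SAP 10.5.2 and 10.5.3).

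Statin use does appear elsewhere:

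- It is a subgroup variable (SAP 7.4), where "the data-derived stratification factor (ie, screening LDL-C level and baseline statin use) will be used" (SAP 10.5.1.3).
- It defines an adverse-event subgroup (SAP 10.6.1).
- It is one of the strata behind the planned check in SAP 10.4: "Difference in stratum assignment between IVRS/IWRS stratum and data-derived stratum will be tabulated".

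No whole-sample efficacy analysis is stated to adjust for it. Two leave the matter open. The CMH test for LDL-C response is adjusted by a stratification factor that is not named (SAP 10.5.2), and the Quade analysis is described only as "Non-parametric analyses (Quade test) will be performed on the FAS and CAS".

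**The concern.** Stratifying on a prognostic factor makes the arms more alike, so the treatment estimate varies less from trial to trial. A model without that factor does not see this. It leaves the between-stratum variation in the residual and reports a standard error larger than the estimate's true variability. Intervals are then too wide, and the test rejects a true null hypothesis less often than its nominal 5%.

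What is at stake is precision, in a trial of 60 patients with 20 on control. The validity of the primary conclusion is not at stake.

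**Working it through.** **Inputs from SAP 3.2.** 40 evolocumab and 20 ezetimibe; 5% never dosed, leaving 38 and 19; SD 20 points; planning effect 20 points; two-sided 0.05; stated power at least 93% per endpoint and at least 85% jointly. Effects in the global study: 37.6 points at week 12 and 36.9 points (31.6 to 42.3) for the mean of weeks 10 and 12.

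**Inputs not in the documents (assumed).** Share of statin users p from 5% to 50%; difference in response between users and non-users d from 5 to 20 points; permuted blocks of 6. The SD of 20 is read as the total SD before adjustment.

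**1. Reproduce the plan's power.** SE = 20 × √(1/38 + 1/19) = 5.62; noncentrality = 20/5.62 = 3.56. Noncentral-t power is 93.8%, which agrees with at least 93%. Jointly, 0.93 × 0.93 = 86.5%, which agrees with at least 85%. The stated power rests on an unadjusted t-test, so it does not depend on the missing term.

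**2. Gain from adding statin use.** Variance explained: R² = p(1-p)d²/20². Adjusted SD = 20√(1-R²). One degree of freedom is spent (54 to 53), which widens the t multiplier by about 0.04%. Example: 0.2 × 0.8 × 10²/400 = 0.04, and √0.96 = 0.980. Power with the LDL-C stratum alone is 93.8% at a 20-point effect.

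| Users p | Difference d | R² | CI narrower by | Power at 20-point effect |
|---|---|---|---|---|
| 10% | 5 | 0.6% | 0.2% | 93.9% |
| 20% | 5 | 1.0% | 0.5% | 94.0% |
| 50% | 5 | 1.6% | 0.7% | 94.1% |
| 10% | 10 | 2.3% | 1.1% | 94.2% |
| 20% | 10 | 4.0% | 2.0% | 94.6% |
| 10% | 15 | 5.1% | 2.5% | 94.8% |
| 30% | 10 | 5.3% | 2.6% | 94.8% |
| 10% | 20 | 9.0% | 4.6% | 95.6% |
| 20% | 20 | 16.0% | 8.3% | 96.8% |

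Share and difference trade off: 10% users with 15 points gain more than 20% users with 10 points.

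**3. Simulation check.** Single-visit linear model, complete data, n = 57, 2 × 2 strata, LDL-C stratum split 50/50 (assumed) and included in both models, 8,000 runs per case. At 20% users and 10 points:

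- Mean model SE with no treatment effect and with a 20-point effect: 5.605 and 5.601 without the term, 5.500 and 5.494 with it, so about 1.9% smaller.
- True SD of the estimate: 5.563 and 5.480 without the term, 5.550 and 5.472 with it, so almost unchanged. The gain is mainly that the reported SE comes into line with variability that stratification had already reduced.
- SE excess without the term: 5.605/5.563 and 5.601/5.480, averaging about 1.5%. A second simulation (20,000 runs per setting, LDL-C at or above 180 mg/dL in 40%, 3 of 60 removed as undosed) also gives 1.5%.
- Mean error of the estimate: at most 0.02 points in either model.

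Type I error, without and with the term: 0.048 and 0.053 at 20% users/10 points; 0.036 and 0.051 at 20%/20 points; 0.028 and 0.053 at 50%/20 points (Monte Carlo SE about 0.0024). Leaving the term out makes the test conservative.

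**4. If statin use has no effect.** In the second simulation the term costs 0.1 to 0.3 power points at the 0.05 level.

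**5. At the effects in the global study.** t-test power at 0.05 without any adjustment is 99.98% at 31.6 points, the lower confidence limit, and above 99.99% at 36.9 and 37.6.

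**The case against.** The case for leaving the plan alone is strong. The model is prespecified, identical in both documents, valid, and errs on the safe side. Every figure for the loss rests on assumed values of p and d. Eligibility generally requires failure of at least two statins (Protocol 4.1.1), so users may be few. Background dosing is stable and the endpoint is a percent change, so their response may differ little. If so, the term does nothing or costs a fraction of a power point. Statin use is also a planned subgroup with an estimated interaction, so its influence will be seen. All of this stands, and it limits the point to a minor one. It does not explain why a factor used to randomise was dropped from the analysis.

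Three stronger readings are tempting, and the documents do not support them.

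- **That tier 1 testing at 0.005 loses meaningful power.** Simulated gains at that level, such as 73.5% to 75.1% at 20% users/10 points, use the 20-point co-primary planning effect and a single p-value. Tier 1 takes the larger of two p-values per pair and applies Hochberg over seven pairs (SAP Table 3), and no tier 1 planning effects are given. At 31.6 points, t-test power at 0.005 is already 99.5%.
- **That the term helps only above a fixed share and a fixed difference.** The gain follows p(1-p)d², so no such pair of cut-offs exists.
- **That the CMH and Quade analyses also omit statin use.** Their factors are not named, and SAP 10.5.1.3 uses the singular term for both factors, so either analysis may include it.

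**Conclusion.** The omission is real and unexplained: two factors in the randomisation, one in the primary model and in the analyses built on it. A reader might infer that the primary result is biased, that type I error is inflated, or that the 93% power claim fails. None of these follows. The simulated estimates, with complete data, are unbiased; the error rate is at or below nominal; and the power claim was computed without covariates.

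What remains is a reported standard error that is slightly too large if statin use predicts response: about 2% of interval width at 20% users/10 points, about 2.5% at 10% users/15 points, and under 1% at a difference of 5 points or less. These sizes depend on assumed p, d and block size, an SD of 20 taken as total, and a single-visit approximation to the repeated-measures model. The co-primary conclusion is very unlikely to turn on it. Severity: minor.

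**What to change.** The model terms should be: treatment group, screening LDL-C level, baseline statin use (yes/no, as randomised in the IVRS/IWRS), scheduled visit, and treatment group by scheduled visit.

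SAP 10.1 records the primary analysis as completed and says the blinded-period analyses will not be repeated, so the planned model should remain primary. Report the extended model once, on the FAS, for the co-primary and continuous co-secondary endpoints. Label it as added after unblinding and outside the confirmatory testing. As a reporting note, the study report should state which stratification factor or factors the CMH test used.

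The cost is one degree of freedom of about 54, one supplementary table and one sentence. The variable and the randomised strata are already held, so no new data or protocol amendment is needed, and no confirmatory result can change.

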3.2 Sample Size

The planned sample size for the comparison between evolocumab and ezetimibe is 40 (20 in Q2W and QM each) and 20 subjects (10 in Q2W and QM each), respectively (60 total). The primary analysis will require the 2-sided tests of each co-primary endpoint to be significant at a level of 0.05. From the global phase 3 study 20110116, the treatment effect of evolocumab compared to ezetimibe for reduction from baseline in

LDL-C at week 12 is at least 37.6% (32.9%, 42.2%) and for the mean of week 10 and 12, 36.9% (31.6%, 42.3%). Assuming 5% of randomized subjects do not receive any IP and with a common standard deviation (SD) of approximately 20%, this study has at least 93% power to detect a treatment effect of 20% or greater reduction for each of the co-primary endpoints in testing the superiority of evolocumab over ezetimibe, based on a two-sided t-test with significance level 0.05.

As the co-primary endpoints are correlated, there is at least 85% (93% x 93%) power to detect significant treatment effects of the co-primary endpoints. The power calculation is derived using nQuery version 7.01.

4. Study Endpoints and Covariates

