10.5.2 Analyses of Secondary Efficacy Endpoints

The statistical model and testing of the tier 1 co-secondary efficacy endpoints will be similar to the primary analysis of the co-primary endpoints. The co-secondary efficacy

endpoints of LDL-C response will be analyzed using the Cochran-Mantel Haenszel (CMH) test adjusted by the stratification factor.

Analyses of the tier 2 co-secondary efficacy endpoints will use the same analysis model as the tier 1 endpoints, and the testing will use a union-intersection test.

Multiplicity adjustment procedures are defined in [Section 10.1](#).

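### The modelled lipid endpoints are adjusted for a two-level screening LDL-C stratum but not for their own continuous baseline, which gives up a modest amount of precision

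*SAP*

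**What the plan says.** SAP 10.5.1.1, with the same text in protocol 10.5.2, lists the model terms: "The repeated measures model will include terms of treatment group, stratification factor of screening LDL-C level, scheduled visit", and treatment by visit. The stratum has two levels, cut at 180 mg/dL (SAP 7.4).

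The model is then reused:
- Tier 1 endpoints use a similar model, apart from LDL-C response, which uses a CMH test (SAP 10.5.2).
- For tier 2: "Analyses of the tier 2 co-secondary efficacy endpoints will use the same analysis model as the tier 1 endpoints".
- ApoA1, the tertiary endpoint, is handled like the co-primary endpoints (SAP 10.5.3).

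SAP 6.2 defines the baseline of each lipid as the mean of the two most recent fasting central-laboratory values up to Study Day 1, or the single value if only one exists. Protocol 10.1.3 allows baseline LDL-C, in its original format, as an optional covariate. SAP 7.4 keeps it only as a median-split subgroup.

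SAP 10.1 describes the primary analysis as completed and says that its blinded-period analyses will not be repeated.

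**The concern.** A cut of screening LDL-C at 180 mg/dL carries part of the information in baseline LDL-C. It may carry almost none of the information in baseline triglycerides, VLDL-C, HDL-C or Lp(a). For those endpoints the model makes little or no adjustment for the subject's starting value of the parameter analysed. For absolute LDL-C change, the stratum is a coarse version of a predictor that is measured on a continuous scale.

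Two things then remain in the treatment estimate. One is chance imbalance between arms in the parameter's baseline, which is easy to get with 19 subjects in one arm. The other is regression to the mean, by which subjects with a high measured baseline tend to fall and those with a low one tend to rise. At stake are the width of the intervals and the conditional accuracy of the secondary estimates. Some of these are tested at demanding levels (tier 1 at 0.005; tier 2 at 0.045 or 0.05).

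**Working it through.** **1. The plan's own figure.** SAP 3.2 plans 40 versus 20 subjects, of whom 5% are not dosed, with SD 20 points. That leaves 40 × 0.95 = 38 and 20 × 0.95 = 19. It states that "this study has at least 93% power to detect a treatment effect of 20% or greater reduction" for each co-primary endpoint, "based on a two-sided t-test with significance level 0.05".

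- SE = 20 × √(1/38 + 1/19) = 5.62 points.
- Noncentrality = 20 / 5.62 = 3.56 on 55 df, which gives power 93.8%. The stated figure reproduces.
- 0.93 × 0.93 = 86.5%, in line with the stated joint power of at least 85%.
- At the earlier global study's effect of 36.9 points, power exceeds 99.99%.

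**2. Size of chance imbalance.** The SE of a between-arm difference in any baseline is √(1/38 + 1/19) = 0.28 baseline SDs. An imbalance of about a quarter of an SD is therefore ordinary.

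**3. A lipid that the LDL-C stratum does not track.** Assumptions (not in the documents): log scale, baseline B is the mean of two readings, outcome Y is one later reading, and all readings have equal variance and common within-subject correlation ρ. In units of that variance:

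- Var(B) = (1+ρ)/2
- Cov(Y−B, B) = ρ − (1+ρ)/2 = −(1−ρ)/2
- Var(Y−B) = 1 + (1+ρ)/2 − 2ρ = 3(1−ρ)/2
- Squared correlation of change with baseline: r² = (1−ρ) / [3(1+ρ)]

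Adding baseline multiplies the residual variance by 1 − r². Estimating one more slope from 57 subjects costs about 1/53, or 2%.

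| ρ (assumed) | r² | r | 1 − r² | after the 2% cost |
|---|---|---|---|---|
| 0.6 | 0.4/4.8 = 0.083 | 0.29 | 0.917 | 0.93 |
| 0.7 | 0.3/5.1 = 0.059 | 0.24 | 0.941 | 0.96 |
| 0.8 | 0.2/5.4 = 0.037 | 0.19 | 0.963 | 0.98 |

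Simulation of percent change (38 versus 19 subjects, 4,000 trials per setting, ρ 0.6 / 0.7 / 0.8) gave variance ratios of 0.92 / 0.965 / 0.98 under one set of assumed values and 0.89 / 0.93 / 0.97 under another. The range is a reduction of 2-11%. HDL-type percent change gave 0.989-0.999.

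The column r also gives the conditional error. A one-SE baseline imbalance moves the unadjusted estimate by r standard errors. With the planning SE of 5.62 points as a stand-in, that is 5.62 × 0.29 = 1.6 points at ρ = 0.6 and 5.62 × 0.19 = 1.1 points at ρ = 0.8.

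**4. Percent LDL-C change.** Here the stratum already carries part of the baseline. A median split of a normal variable (assumed) captures 2/π = 64% of it, so the ratio is (1 − r²)/(1 − 0.64r²). With r² = 0.037 this is 0.963/0.976 = 0.986. The 2% cost of the extra slope cancels that, which leaves a gain of about 0-1%. If change were unrelated to baseline, the SE would rise slightly (5.65 to 5.70 in simulation).

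**5. Absolute LDL-C change.** Simulated variance ratios for assumed baseline SDs of 30 / 45 / 60 / 75 mg/dL were 1.00 / 0.97 / 0.96 / 0.95 under one set of assumptions and 0.96 / 0.94 / 0.93 / 0.90 under another. The range is a reduction of 0-10%.

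**The case against.** The strongest reply is that percent change already divides by the subject's own baseline, and that every modelled endpoint except absolute LDL-C change is a percent change. This is why percent LDL-C and HDL-C change gain almost nothing, and that part stands. Division does not remove regression to the mean, however: step 3 shows that change on the ratio scale is still correlated with a noisy baseline.

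A second reply is that the sizes depend on unstated inputs. That is also right, and only ranges are claimed. A third is that protocol 10.1.3 already permits covariate analyses. It permits them without planning any, and its list names baseline LDL-C but not the other lipids' own baselines. The sensitivity analyses in SAP 10.5.1.2 concern the co-primary endpoints only.

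Some stronger readings are tempting, but the documents do not support them:

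- **A large loss of precision.** If percent change correlated 0.5 with its own baseline, a lipid unrelated to the stratum would gain 25% (1 − 0.5²). The documents give no such correlation. In the model of step 3 it requires 0.25 = (1−ρ)/[3(1+ρ)], so ρ = 0.25/1.75 = 0.14, meaning that a subject's repeat readings barely agree.
- **Dose frequency wrongly omitted.** Allocation is 2:2:1:1, so frequency is balanced in both pooled arms and leaving it out causes no bias. The SAP does not say whether treatment group means two pooled groups or the four arms; with four, frequency is already in the model. SAP 10.5.1.4 also plans frequency-specific comparisons.
- **All continuous endpoints affected.** The exploratory lipid endpoints are only described (SAP 10.5.4), so no model applies to them.

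**Conclusion.** The point holds as a minor improvement. Every modelled continuous endpoint is adjusted for one dichotomised LDL-C value and none for its own continuous baseline, although that baseline is defined and collected. The expected reduction in the variance of the treatment estimate is 2-11% for triglyceride-type percent change, 0-10% for absolute LDL-C change and about 0-1% for percent LDL-C and HDL-C change. These ranges assume within-subject correlations of 0.6-0.8 for triglyceride-type measures and baseline LDL-C SDs of 30-75 mg/dL; the documents supply neither.

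A reader might infer that the co-primary result is fragile. It is not: the stated power reproduces at 93.8%, and those two endpoints gain least from the change. The value lies in showing whether the secondary estimates depend on baseline imbalance in a small control arm.

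**What to change.** For each modelled continuous endpoint, add the analysed parameter's own continuous baseline and its interaction with visit. Use the log scale for triglycerides, VLDL-C and Lp(a). Keep the screening LDL-C stratum. No dose-frequency term is needed.

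Under the current SAP version, report this as a supplementary baseline-adjusted analysis beside the pre-specified result, which stays as it is. Label it as added after the primary analysis.

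The cost is one extra term and its visit interaction, with no new data. The SAP does not say which visits enter the model. If all four post-baseline fasting-lipid visits are used (weeks 2, 8, 10 and 12), this adds 1 + 3 = 4 parameters. For the apolipoproteins and Lp(a), measured at weeks 10 and 12, it adds 1 + 1 = 2.
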